### Abstract

28 While cardiac rehabilitation has been shown to be effective at improving coronary heart disease, participation is generally poor. For this reason, the current research, a prospective, randomized 29 controlled pilot study, will evaluate the impact of a social media intervention on motivation for 30 31 exercise and adherence to cardiac rehabilitation. Participants will be recruited from the inpatient 32 setting, during their intake visit to cardiac rehabilitation, or via phone call. They will then be randomly assigned to a private Facebook group or a comparison group. This study is grounded 33 in self-determination theory. The intervention will include access to a private Facebook group 34 35 in which participants will receive weekly educational posts, provider support and have the 36 opportunity to communicate with other cardiac rehabilitation patients. Postings and peer support are designed to enhance self-determined motivation through support of autonomy, competence 37 38 and relatedness. Patients in the comparison group will be given the same educational and provider materials, but these will be supplied in handout form, or email if the patient is absent 39 from cardiac rehabilitation. Participants will be asked to fill out a pre-post Behavioral 40 Regulation in Exercise Questionnaire-3, to measure self-determined motivation, and The 41 Psychological Need Satisfaction for Exercise Scale to measure fulfillment of needs that affect 42 motivation. The total number of sessions attended at the end of 3 months will be tallied and 43 analyzed using t-tests. Overall motivation will be evaluated using analysis of covariance models. 44 Multivariate analysis of variance models will be used to evaluate differences in the change across 45 motivation subtypes. If significant, ANCOVA models for each subtype will be fit. ANCOVA 46 models will be used to compare changes in needs satisfaction, overall and separately among the 47 three subscales, between groups. Engagement in the Facebook group will be measured by 48 counting number of "likes" and self-report of weekly use ("hits"). The researchers will enroll 30 49

50	participants in each group. Engagement in the Facebook group and participation in the study
51	will help to determine the feasibility of using Facebook to affect adherence and motivation in
52	cardiac rehabilitation patients, potentially improving outcomes through the use of a unique
53	intervention.
54	Key words: Cardiac rehabilitation, social media, adherence, motivation, Facebook, self-
55	determination theory, Behavioral Regulation in Exercise Questionnaire, Psychological Need
56	Satisfaction in Exercise Scale
57	
58	
59	
60	
61	
62	
63	
64	
65	
66	
67	
68	
69	
70	
71	
72	
73	
74	
75	
76	

77	
78	Feasibility of a Facebook Intervention for Exercise Motivation and
79	Cardiac Rehabilitation Adherence: A Study Protocol
80	Introduction
81	Background
82	Coronary Heart Disease (CHD) is the leading killer of men and women and currently

accounts for 15.5 million cases in the United States [1]. Phase II cardiac rehabilitation, a Class-1 83 recommendation by the American College of Cardiology Foundation and the American Heart 84 Association, is a secondary prevention program that has been shown to be safe and effective in 85 treating patients diagnosed with existing CHD [2, 3, 4, 5, 6, 7, 8, 9, 10]. However, despite the 86 87 reported effectiveness of cardiac rehabilitation, many at high risk for CHD are less likely to adhere to the program [11]. Utilization of cardiac rehabilitation is low overall, particularly for 88 women, minorities and those with comorbidities [4], and attempts to increase uptake and 89 90 adherence often fail [12].

In recent years, web-based interventions have been used to examine exercise adherence, 91 and theory-supported apps have enabled feedback on exercise intensity and adherence in 92 remotely-delivered cardiac rehabilitation [13]. Interventions utilizing the web improved daily 93 step counts [14] and physical activity intensity [15]. The use of such applications has been 94 shown to be feasible and acceptable for use in special populations, including patients with cystic 95 fibrosis [16] and cancer survivors [17]. A recent randomized controlled trial utilizing online 96 social media to test its effect on physical activity found that the social support provided by the 97 98 program resulted in an increase in group cohesion [18]. The perception of group cohesion may be important to patients in cardiac rehabilitation since social support was found to be an 99

important component in exercise adherence [19]. Due to the vital role that social support has
played in helping people to become more self-motivated [20], it is appropriate to examine unique
ways to foster a sense of belonging or connectedness.

Social media is growing in popularity, making it an interesting venue for delivery of an 103 intervention designed to affect cardiac rehabilitation adherence. Facebook in particular has the 104 105 most engaged users of all social media sites, with 70% logging in daily [21]. Social networking 106 on the web, such as Twitter or Facebook, has helped patients manage personal health and increased adherence to medical treatment [22], possibly through a sense of involvement and 107 108 social support. Joseph, Keller, Adams, and Ainsworth [15] showed pilot data that supports Facebook as a tool for promoting physical activity by utilizing education and group discussions. 109 Facebook, relative to other social media or web-based interventions, has been reported to have 110 111 high retention rates when used to affect health behaviors [23]. While Facebook has been studied as a means to improve physical activity in a number of populations [16, 17, 24, 25, 26, 27], there 112 is a knowledge gap regarding the effectiveness of social networking interventions used to 113 promote health [28] and its use in cardiac rehabilitation as a tool to improve motivation. 114

### **115** Theoretical Framework

The current study is grounded in self-determination theory [29, 30, 20] which defines motivation in terms of intrinsic and extrinsic sources (**Figure 1**). Self-determination theory focuses on social and cognitive factors and how those factors influence an individual's motivation. The theory describes motivation as being on a continuum, with behavioral regulators ranging from amotivation, in which a person lacks intention to do an activity, to intrinsic motivation in which an individual may do the activity simply for the joy of it [20]. Selfdetermination theory specifically examines conditions that lead to self-determined motivation

123	(internalized) and states that 3 psychological needs are necessary for it to exist: competence,
124	autonomy and relatedness [20]. A motivationally supportive environment supports these three
125	needs in several ways. Competence, in essence self-efficacy, can be supported through provision
126	of structure, offering participants positive feedback and helping them to set realistic goals [31,
127	32, 33]. Competence, according to Cognitive Evaluation Theory, a sub-theory of self-
128	determination theory, will not lead to intrinsic motivation in the absence of autonomy [34].
129	Autonomy may be supported by helping the individual make decisions for personal reasons and
130	helping them to make choices with minimal pressure [31, 32, 33]. Relatedness can be promoted
131	by providing a sense of connectedness to others. An environment that helps a person feel
132	socially included and supported by others may help facilitate intrinsic motivation [20, 32, 35].
133	Motivation for exercise is an important concept in the examination of cardiac
134	rehabilitation adherence. Self-determination theory was previously used as a theoretical
135	framework for motivational research in a cardiac rehabilitation setting [36]. Thorup and
136	colleagues [36] showed qualitative evidence that a pedometer-based cardiac rehabilitation
137	intervention supported autonomy, competence, and relatedness. It is possible that increasingly
138	more self-determined motivation (internalized) may be enough to help patients overcome the
139	many obstacles associated with non-adherence to exercise and cardiac rehabilitation.

140 **Figure 1.** Self-Determination Theory

Amotivation; External Regulation; Introjected Regulation; Identified Regulation; Integrated Regulation; Intrinsic Regulation

Increasingly More Self-Determined

142

143

# 144 Study Objectives

The purpose of the current randomized pilot trial is to determine the feasibility of using a Facebook intervention, providing education, peer support and provider support, to affect change in motivation and self-determination for exercise, and adherence to cardiac rehabilitation in patients with CHD during a 12-week Phase II cardiac rehabilitation program. It is hypothesized that:

150	1.	Scores for motivation for exercise overall will increase for patients exposed to a
151		Facebook intervention and across individual motivational subtypes (regulations)
152		relative to a comparison group who receive educational handouts and emails.
153	2.	Percentage of cardiac rehabilitation sessions attended will be higher relative to a
154		comparison group who receive educational handouts and emails.
155	3.	Engagement in the private Facebook group (number of "hits" and "likes") will predict
156		number of cardiac rehabilitation sessions attended and the change in motivation. The
157		feasibility of a larger trial will be based on sample size and participants' engagement
158		in the Facebook group.
159		
160		
161		

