190 The primary hypothesis, change in motivation for exercise, will be measured at baseline and post-intervention using the BREO-3. The BREO-3 is a 24 question validated instrument that 191 measures forms of intrinsic and extrinsic regulation of exercise behavior [34] and is based on 192 193 self-determination theory. Psychometrics were first completed for the BREQ-2 by Markland and Tobin [38]. Cronbach's alpha reliabilities were as follows: amotivation = 0.83, external 194 regulation = 0.79, introjected regulation = 0.80, identified regulation = 0.73, and intrinsic 195 regulation = 0.86. The BREO-3 includes 5 additional questions in addition to those on the 196 BREQ-2 and has a new subscale for integrated regulation [33]. The subscales (regulations) of 197 the BREQ-3 are used to calculate a relative autonomy index (RAI) [39]. Each question is 198 answered on a 5 point Likert scale (0-4) and represents one of the regulations. The regulations 199 are weighted then summed to give a single score. The resulting score or index gives an 200 201 indication of the individual respondent's self-determination for exercise.

The RAI will place individual motivational subtypes or behavioral regulations on the self-determination continuum from amotivated (lacking intention to exercise) to intrinsically motivated (self-determined or autonomously motivated).

The PNSE will be used to assess need satisfaction with exercise. This scale was designed to assess the perception of psychological need satisfaction associated with self-determined

207	motivation for exercise and consists of 18 items on a 6 point Likert scale, with 3 subscales
208	measuring perceived competence, autonomy, and relatedness. The scale showed high internal
209	consistency (Cronbach >0.90) [37].

The secondary hypothesis, the percentage of cardiac rehabilitation sessions attended, will be measured at the time of cardiac rehabilitation completion or dropout. It will calculated by dividing the number of sessions attended in a 3 month period of time by the total number of sessions allowed by insurance, and multiplying by 100.

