# 336 Data Analysis

337	Statistical Methods. This is a feasibility study and the sample size obtained will determine if
338	the study is appropriately powered to detect the desired effect size. Patient characteristics will be
339	summarized by group using frequencies and percentages for categorical factors, and means and
340	standard deviations for continuous measures. In order to examine the primary outcome,
341	differences in change in motivation between groups, overall motivation using the RAI from the
342	BREQ-3 will be evaluated using analysis of covariance (ANCOVA) models. Mean differences
343	with 95% confidence intervals for group differences will be presented. Multivariate analysis of
344	variance models will be used to evaluate differences in the change across individual motivation
345	subtypes (regulations), using the BREQ-3, between groups overall. If significant, separate
346	ANCOVA models for each subtype will be fit. Similar ANCOVA models will be used to
347	compare changes in needs satisfaction scores, overall and separately among the three subscales,
348	between groups. Two-sample t-tests will be used to compare number of sessions completed. As
349	a secondary analysis, the relationships between patient characteristics, "hits" and "likes", and the
350	outcome variables RAI change, number of sessions, and needs satisfaction change will be
351	examined using t-tests and Pearson correlations. The correlation between changes in RAI and

352	needs satisfaction will also be evaluated. Analyses will be performed using SAS software
353	(version 9.4; Cary, NC). An overall significance level of 0.05 will be assumed for all tests.
354	Sample Size. The investigators plan to enroll 30 patients in each group. In the first 9 months of
355	2016, cardiac rehabilitation at the main campus of this tertiary care center had approximately 170
356	patient intakes. It is assumed that there will be a similar number of patient intakes for a 9 month
357	period in 2017. Based on Facebook participation rates for those over age 50 [21] and the high
358	participation rates in previous research projects in this facility's cardiac rehabilitation, it is
359	estimated that 40% may meet eligibility requirements and agree to participate. Allowing for use
360	of the first 8 participants to establish the Facebook group, the estimated sample size would then
361	be 60 total participants for randomization to study group who can then be included in

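### Do the blanket increase predicted across regulations in hypothesis 1 and the unrestricted 86% power figure need correcting for the subtype analysis?

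*Combined protocol and SAP*

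**What the plan says.** All references are to the combined protocol and SAP.

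- **Study Objectives, hypothesis 1:** "Scores for motivation for exercise overall will increase for patients exposed to a" "Facebook intervention and across individual motivational subtypes (regulations"), relative to the comparison group. No direction is given per regulation.
- **Theoretical Framework:** Figure 1 orders the regulations as "Amotivation; External Regulation; Introjected Regulation; Identified Regulation; Integrated Regulation; Intrinsic Regulation" and labels the sequence as one of growing self-determination. The text describes "amotivation, in which a person lacks intention to do an activity".
- **Measures:** the relative autonomy index (RAI) is a weighted sum of the BREQ-3 regulations, placed on a "self-determination continuum from amotivated (lacking intention to exercise) to intrinsically motivated".
- **Data Analysis, Statistical Methods:** the RAI is compared by ANCOVA with no precondition. Change across the regulations is compared by MANOVA, and only if that is significant will separate "ANCOVA models for each subtype will be fit". The significance level is 0.05 for all tests.
- **Data Analysis, Sample Size:** 30 per group is said to give 86% power at d = 0.8 for the study outcomes, with no test or outcome named. The next sentences give feasibility and estimation as the purpose of the sample size, and the wish for a large enough Facebook group as the main reason for choosing 30.
- **Study Objectives, hypothesis 3:** the "feasibility of a larger trial will be based on sample size and" engagement in the group.

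**The concern.** Two things catch the eye.

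First, amotivation is on the protocol's own list of regulations and means a lack of intention. A prediction that scores rise across the regulations therefore includes, read literally, a prediction that the intervention makes people less inclined to exercise. If that reading governed, an unfavourable result could be counted as support, and nothing would fix in advance which subtype findings confirm the hypothesis.

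Second, the regulations belong to the first hypothesis, so the unrestricted power statement seems to cover them. But a subtype result needs two successes, the MANOVA and then that subtype's ANCOVA, and the sample-size section mentions neither the screening step nor the number of outcomes. A reader might apply 86% to an analysis for which it was not calculated.

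**Working it through.** **Direction.** Set the passages side by side. Hypothesis 1 names neither amotivation nor every regulation; the conflict arises only when it is combined with Figure 1 and Measures. Those same sections give the intended direction: the continuum starts at amotivation and moves toward intrinsic regulation as self-determination grows, and the RAI condenses it into one self-determination score. The MANOVA has no direction and an ANCOVA estimate carries its own sign, so the wording of the hypothesis enters no calculation.

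**The stated 86%.** Inputs from Sample Size and Statistical Methods: n = 30 per group, d = 0.8, alpha 0.05. Two-sided testing is assumed, since the text does not say. Noncentrality is 0.8 × √(30/2) = 3.098 on 58 degrees of freedom. Power is 86.1%, which reproduces the figure. A one-sided test would give 92.2%.

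**The MANOVA step.** With two groups and six outcomes this is Hotelling's T², referred to F(6, 53), with noncentrality λ = 15 × δ′R⁻¹δ. Here δ holds the shifts in SD of change and R the between-subscale correlations. The documents give neither, so both are assumptions. With a common correlation r and 15 × 0.64 = 9.6:

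- One subscale shifted: λ = 9.6(1 + 4r) / [(1 − r)(1 + 5r)].
- All six shifted the same way: λ = 57.6 / (1 + 5r).
- Amotivation down, with identified, integrated and intrinsic regulation up: λ = 38.4(1 + 4r) / [(1 − r)(1 + 5r)].
- The same four shifts, but with amotivation correlated −r with the other three and external and introjected regulation uncorrelated with these four: λ = 38.4 / (1 + 3r).

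| Pattern | r = 0 | r = 0.3 | r = 0.5 | r = 0.7 |
|---|---|---|---|---|
| One shifted: λ | 9.60 | 12.07 | 16.46 | 27.02 |
| One shifted: power | 56% | 68% | 83% | 97% |
| All six: λ | 57.6 | 23.04 | 16.46 | 12.80 |
| All six: power | >99.9% | 95% | 83% | 71% |
| Four shifted, common r: λ | 38.4 | 48.3 | 65.8 | 108.1 |
| Four shifted, common r: power | 99.8% | >99.9% | >99.9% | >99.9% |
| Four shifted, other structure: λ | 38.4 | 20.21 | 15.36 | 12.39 |
| Four shifted, other structure: power | 99.8% | 91% | 80% | 69% |

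The last two pairs of rows use the same effects. Only the correlation structure differs, and power at r = 0.7 moves from near certainty to 69%.

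**MANOVA and the subtype's own test together.**

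- Below 86%: with one subscale shifted and r = 0, the joint chance cannot exceed the 56% of the MANOVA. With t-tests standing in for the ANCOVAs, simulation gave 55/65/76/85% for r = 0/0.3/0.5/0.7.
- Above 86%: the plan uses ANCOVA. For an assumed baseline-to-post correlation of 0.3 to 0.7, a single ANCOVA has about 91–97% power if d is in SD of change, and about 89–99% if it is in raw SD. Take the lowest value on the SD-of-change scale, 91.0%, with a MANOVA power of 99.8%. The joint chance is then at least 91.0 + 99.8 − 100 = 90.8%.

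So 86% is neither a ceiling nor a floor for the subtype analysis.

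**The case for a change.** The strongest case for a change is that it would be cheap and could be credible only before results are seen. The intended sign for amotivation can be inferred, but for external and introjected regulation, in the middle of the continuum, the documents do not settle it. A significant MANOVA does not show an increase, so support for the subtype part of hypothesis 1 is left to judgement. On power, passing the MANOVA and then a given test can never be more likely than passing that test alone, and the pilot is meant to inform a larger trial that might inherit both sentences.

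Much of this is true. The signs for the two middle regulations are not stated, and the 86% was not worked out for the subtypes. But the first point concerns how a secondary breakdown in a pilot would be described, not how it would be analysed. On the second, screening does cost power relative to the same test unscreened, yet that test is an ANCOVA whose power may exceed 86%. A d of 0.8 is in any case a measure for one two-group comparison, and the sample-size text makes no claim about the MANOVA. The larger trial would need its own power calculation, which this section anticipates by looking ahead to smaller differences.

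**Conclusion.** No change follows. The wording of hypothesis 1 is loose for amotivation, but the protocol's framework supplies the favourable direction for that subscale. No planned test depends on a sign, and the RAI comparison stands apart from the subtype analysis. An analyst would read a rise in amotivation as unfavourable.

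The 86% is right for what it describes: one two-sided two-group comparison with 30 per arm and complete data (86.1%). For the screened subtypes it is simply not derived. Their power may lie on either side of 86%, with the MANOVA step ranging from about 56% to over 99% in the scenarios above. That range rests wholly on assumed correlations and effect patterns, so no corrected single figure can be taken from the documents.

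Nothing is decided on subtype power. Going on to a larger trial depends on sample size and engagement, and 30 per group was chosen mainly to make the Facebook group workable. Stating signs and limiting the power sentence to a single comparison such as the RAI would read better, but would leave every model, test, sample size and conclusion as it is.

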### Methodology

### 164 Design

165 This is a prospective, randomized controlled pilot trial to evaluate the feasibility of using 166 a social media intervention to affect change in motivation for exercise and adherence to cardiac 167 rehabilitation sessions.

#### 168 Setting and Sample

The setting for this study will be in the outpatient cardiac rehabilitation at the main 169 170 campus of a large tertiary care center in Northeast Ohio and several satellite facilities in the region, and in patients' homes or other locations where home computers might be accessed. This 171 cardiac rehabilitation program provides ECG-monitored, supervised exercise, dietary guidance, 172 smoking cessation, behavioral counseling and stress reduction. All patients receive an 173 individualized exercise prescription based on functional capacity at intake. Most patients, 174 depending on insurance coverage, will be able to attend up to 3 sessions per week for a total of 175 36 sessions. In addition, patients are given guidance for unsupervised exercise at home. 176

177 All patients who are current and regular Facebook users, have qualified for cardiac 178 rehabilitation (diagnosed with CHD), and are entering cardiac rehabilitation at the main campus 179 of this tertiary care center, will qualify to participate in the study prior to beginning Phase II cardiac rehabilitation. Current Facebook users were chosen as it is important that participants 180 181 are skilled at using the internet and familiar with social media. Regular use will be defined as logging onto Facebook at least 2 times in the last month. Inclusion criteria will include both men 182 and women 18 years of age or older who speak English and live within 100 miles of the main 183 campus of this tertiary care center. Participants must be able to read and understand English in 184

order to read the information sheet and complete the Psychological Need Satisfaction in Exercise
Scale (PNSE) [37] and the Behavioral Regulation in Exercise Questionnaire-3 (BREQ-3). There
will be no exclusion based on secondary diagnosis; however, participants must be able to
exercise well enough to qualify to take part in cardiac rehabilitation.

189 Measures

190 The primary hypothesis, change in motivation for exercise, will be measured at baseline and post-intervention using the BREO-3. The BREO-3 is a 24 question validated instrument that 191 measures forms of intrinsic and extrinsic regulation of exercise behavior [34] and is based on 192 193 self-determination theory. Psychometrics were first completed for the BREQ-2 by Markland and Tobin [38]. Cronbach's alpha reliabilities were as follows: amotivation = 0.83, external 194 regulation = 0.79, introjected regulation = 0.80, identified regulation = 0.73, and intrinsic 195 regulation = 0.86. The BREO-3 includes 5 additional questions in addition to those on the 196 BREQ-2 and has a new subscale for integrated regulation [33]. The subscales (regulations) of 197 the BREQ-3 are used to calculate a relative autonomy index (RAI) [39]. Each question is 198 answered on a 5 point Likert scale (0-4) and represents one of the regulations. The regulations 199 are weighted then summed to give a single score. The resulting score or index gives an 200 201 indication of the individual respondent's self-determination for exercise.

The RAI will place individual motivational subtypes or behavioral regulations on the self-determination continuum from amotivated (lacking intention to exercise) to intrinsically motivated (self-determined or autonomously motivated).

The PNSE will be used to assess need satisfaction with exercise. This scale was designed to assess the perception of psychological need satisfaction associated with self-determined

207	motivation for exercise and consists of 18 items on a 6 point Likert scale, with 3 subscales
208	measuring perceived competence, autonomy, and relatedness. The scale showed high internal
209	consistency (Cronbach >0.90) [37].

The secondary hypothesis, the percentage of cardiac rehabilitation sessions attended, will be measured at the time of cardiac rehabilitation completion or dropout. It will calculated by dividing the number of sessions attended in a 3 month period of time by the total number of sessions allowed by insurance, and multiplying by 100.

The tertiary hypothesis, Facebook engagement, will be assessed by measuring the 214 215 number of "likes" by individuals on the private Facebook group. "Likes" (the number of times a participant clicks "like" on any of the Facebook posts) will be counted and, along with "hits" 216 will be used to examine the association between engagement in the social media intervention 217 (Facebook), and cardiac rehabilitation adherence and change in motivation. A post-intervention 218 questionnaire will be given to determine number of "hits". The participants will be asked to 219 220 circle the number of times they accessed the private Facebook group per week: 0, 1-5, 6-10, 11-15 or > 15 times. The questionnaire will also be used to collect qualitative data on participants' 221 perceptions of the intervention, including whether they felt supported in their care, more in touch 222 223 with providers, whether or not they chatted with other Facebook members and if the Facebook group affected their exercise behaviors. The questionnaire will use a Likert scale (1, "not at all"-224 5, "quite a bit") for all questions in addition to a section for comments. Participants may also 225 grant permission for the evaluation of comments made on the private Facebook group, allowing 226 the researchers to explore themes for qualitative analysis. Examination of comments will allow 227 for a better understanding of the effectiveness of individual posts and the satisfaction of needs 228 that may lead to self-determined motivation. 229

Patient characteristics will be collected and will include key demographic variables (age,
gender, race, employment, distance to cardiac rehabilitation, socioeconomic status), engagement
(number of "hits" and "likes"), and key clinical variables (cardiac rehabilitation indication,
hypertension, diabetes, hyperlipidemia and waist circumference), which will be obtained from
the electronic medical record.

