a. Educational posts will cover 12 topics that will encourage participants to practice 297 298 preventive heart care while offering a variety of suggestions and encouragement 299 for making personal healthcare choices. The educational portion of the intervention is designed to offer clear information and structure, thus supporting 300 301 competence which may help to enhance intrinsic motivation. These 12 educational topics will be standardized such that they will be posted on the 302 Facebook group, one each week and then the same ones will be re-posted again 303 every 12 weeks. The posts may be in the form of text, video and/or pictures and 304 will include materials from the hospital's health library and other fact sheets and 305 videos produced by the hospital, the American Heart Association and the Center 306 for Disease Control. 307

b. Provider posts will include topics such as motivational quotes, encouragement,
reminders to exercise independently, and reminders to contact providers with
questions. These postings are designed to promote a sense of choice and help
participants feel that providers see them as having a unique frame of reference
thus being autonomy-supportive. Providers will be nurses on the research team,

313	exercise physiologists and nurse practitioners and physicians who may or may not
314	choose to reveal personal identities. All Facebook participants will see the same
315	content. Provider support will also include links to provider health chats, in
316	which patients can chat online with providers at set dates and times.
317	c. Peer interaction on Facebook will be as frequently as the participant freely
318	chooses to do so and will be monitored daily by the research team for
319	appropriateness of content. Engagement in Facebook is designed to offer an
320	opportunity for social inclusion and a sense of involvement, allowing for
321	relatedness.
322	The comparison group will receive the same educational and provider support materials
323	as the Facebook group but will receive it in the form of a handout, or via email in the event the
324	patient cannot be contacted or misses cardiac rehabilitation on a particular week. Both groups
325	will have the opportunity for weekly education classes and typical peer interactions, which will
326	involve up to 3 hours of group cardiac rehabilitation per week.
327	Upon cardiac rehabilitation completion or dropout, post-data will be collected. It is

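### Minor, cheap to improve: the self-reported 'hits' item is coarse at the low end, so it may separate participants poorly if most visit the group only a few times a week

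*Combined protocol and SAP*

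**What the plan says.** Measures: 'hits' comes from a single self-report ("questionnaire will be given to determine number of 'hits") after the intervention. Participants "circle the number of times they accessed the private Facebook group per week: 0, 1-5, 6-10", continuing with "11-15 or > 15 times". That makes five boxes. 'Likes' is obtained differently: each time a "participant clicks 'like' on any of the Facebook posts) will be counted".

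Study Objectives, hypothesis 3: "Engagement in the private Facebook group (number of 'hits' and 'likes') will predict" sessions attended and change in motivation. The same item bases the feasibility of a larger trial on sample size and engagement.

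Statistical Methods: the relationships of 'hits' and 'likes' with RAI change, sessions and needs satisfaction are a secondary analysis by t-tests and Pearson correlations. No scoring of the five boxes is given.

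Three other places bear on how often the group might be visited:
- Setting and Sample sets the eligibility floor for regular use at "logging onto Facebook at least 2 times in the last month".
- Data Collection Procedures puts the educational posts on the "Facebook group, one each week and then the same ones will be re-posted again" on a 12-week cycle. It adds provider posts with no stated frequency ("Provider posts will include topics such as motivational quotes, encouragement" and reminders), unrestricted peer interaction, and text prompts for new posts.
- The Introduction cites 70% of Facebook users logging in daily.

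No expected access rate for the study group is stated. Limitations and Unanticipated Problems admits reporting bias in 'hits' but does not mention the width of the boxes.

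**The concern.** Someone who opens the group every second week has no true answer. That person must choose between 0, which is also the answer of a participant who never looked, and 1-5, which is also the answer of someone who looked almost every day. For a pilot meant to learn about engagement, this is the part of the scale where detail is most useful. Yet three of the five boxes are reserved for six or more visits per week.

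If most participants fall in one box, the correlations of 'hits' with attendance and RAI change shrink, and a null result says little. 'Likes' does not fully replace 'hits', because a participant can read posts without clicking. The detail cannot be recovered once the questionnaire has been completed. In addition, a Pearson correlation needs numbers, and unequal boxes with an open top have no obvious ones.

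**Working it through.** **The plan's own figure.** Sample Size states 86% power for d=0.8 with 30 per group. The noncentral t with df=58, noncentrality 0.8 × √15 = 3.10 and two-sided 0.05 gives 0.861, so the figure is reproduced. It concerns the two-group comparison. The plan states no power for the Hypothesis 3 correlations.

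**Inputs from the plan.** Box limits 0, 1-5, 6-10, 11-15, >15 (Measures); 30 participants with 'hits' data, since only the Facebook arm has them; alpha 0.05 (Statistical Methods), taken as two-sided.

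**Assumptions, not in the plan.** Weekly visits are log-normal with median m and log-SD s. Answers are rounded to whole visits and boxes are scored 0-4. The true correlation of the outcome with log use is 0.5. Recall is without error unless stated.

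**Step 1: share in the 1-5 box.** Share = Φ[(ln 5.5 − ln m)/s] − Φ[(ln 0.5 − ln m)/s].
- m=2, s=0.6: Φ(1.69) − Φ(−2.31) = 0.954 − 0.010 = 0.94.
- m=3, s=1.0: Φ(0.61) − Φ(−1.79) = 0.728 − 0.037 = 0.69.

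These are the extremes for m=1-3 and s=0.6-1.0.

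**Step 2: attenuation and power.** The observed correlation is 0.5 × corr(box score, log use), the latter by simulation. Power = Φ[√27 × artanh(r) − 1.96].
- Exact count, r=0.50: Φ(2.85 − 1.96) = 0.81.
- Worst case, m=2, s=0.6, r=0.263: Φ(1.40 − 1.96) = 0.29.
- Best case, m=3, s=1.0, r=0.41: Φ(2.26 − 1.96) = 0.62.

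**Step 3: finer boxes.** Options: never, less than once a week, 1, 2, 3, 4-5, 6-10, 11-15, >15.

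| Median visits per week | Share in 1-5 box | Power, plan's boxes | Power, finer boxes |
|---|---|---|---|
| 0.5 | about 50% | 59-62% | no dependable gain |
| 1-3 | 69-94% | 29-62% | about 73-79% |
| 5 | 53-56% | 65-68% | 78-79% |
| 7 | 35-40% | 71-73% | 77-78% |
| 10 | 16-28% | 72-75% | 75-76% |

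The low end of the finer-box range depends on scoring. At a median of 1 it is about 69% if every value below one visit goes into a single box. At 0.5 the result can move either way with how participants choose between never and less than once a week.

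**Step 4: sensitivity.** Widening s to 0.5-1.2 at medians 1-3 gives 62-98% in the 1-5 box and power of 18-67%. In the most concentrated case (m=2, s=0.5), the chance that all 30 choose the same box is about 0.47; at medians of 5 or more it is about 0. With an assumed recall error of log-SD 0.8 at medians 1-3, power is about 24-45% with the plan's boxes. With a finer set whose top box is more than 10, it is about 31-53%, a gain of about 6-10 points.

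All power figures are for Pearson correlation of the box scores. Spearman's test was not simulated for power.

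**The case against.** The strongest reply is that nothing in the plan says how often participants will open the group. A reader might infer that 'hits' is bound to show almost no variation. The documents do not support that: at medians of 7-10 visits the existing boxes spread participants reasonably, and the finer set adds only a few points.

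A reader might also argue that the boxes contradict the weekly posting schedule or the eligibility rule. Neither follows. Only the educational posts are weekly; provider posts, peer interaction and text prompts could all raise visits. The eligibility rule is a pre-enrolment floor for Facebook in general, not an expected rate for a prompted study group. Equally, the 70% daily log-in figure describes general Facebook use and does not show that this group will be visited daily.

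Nor does Hypothesis 3 lose its only predictor, because 'likes' is an ungrouped count. The analysis is tertiary in Measures and secondary in Statistical Methods, in a pilot that claims no power for it. Recall error, which the plan partly acknowledges as reporting bias, would reduce the benefit of finer boxes.

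All of this stands and keeps the point minor. It leaves untouched the missing option between 0 and 1, the width of the 1-5 box, and the absence of a scoring rule.

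**Conclusion.** The item is coarse where low and moderate users would need to be told apart. That can be read directly from the response options. How much it costs is conditional. At a median of 1-3 visits per week, with the assumptions above and perfect recall, power for a true correlation of 0.5 is about 29-62%, against about 73-79% with finer low-end boxes and 81% with exact counts. At a median of 5 the gain is about 10-14 points (65-68% to 78-79%). At 7-10 it is a few points, at about 0.5 no gain can be claimed, and with recall error it is smaller throughout. The primary analysis and the stated 86% power are unaffected. This is a cheap improvement to a secondary measure, not a flaw that undermines the trial.

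**What to change.** Before the questionnaire is used, change the options to: never, less than once a week, 1, 2, 3, 4-5, 6-10, 11-15, more than 15 times per week. Asking for a number would also do. Keep the upper boxes, so that nothing is lost if use proves high. In Statistical Methods, replace Pearson with Spearman correlation for 'hits'; this removes the need to give numbers to unequal boxes, though it does not restore detail lost to grouping.

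The cost is one edited line in a study questionnaire, one edited sentence in the analysis section, and slightly more recall effort for participants. No extra visit or data source is needed. Counting participants' comments as a further engagement measure is not part of this recommendation: Measures makes evaluation of comments depend on participants' permission, so a count should be added only if that permission covers it.
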